8 STATISTICAL METHODOLOGY AND STATISTICAL ANALYSES

8.1 STATISTICAL METHODS

Analyses will be conducted separately for each country and the final report will consist of three parts: one part for Italy, one part for Spain, and the final part with pooled data of both countries. Pooling of data for the combined results of Italy and Spain will be done at the patient level. ICD9 codes of the Italian data will be mapped unto ICPE codes of the data from Spain. ICD9 codes that do not map directly to ICPE will be noted and the frequency of patients with outcomes in these unmapped categories will be reported. Given the very low enrolment from Italy (approximately 40 patients, vs. approximately 1700 from Spain) very few patients/outcomes from Italy are likely to be reported as unmapped. Assessment and adjustment for confounding will be done separately for each country and also done separately for the pooled analyses and follow the same methodology in the individual and pooled analyses. All statistical analyses will be performed using the SAS software 9.2, running with SAS Enterprise Guide 4.3, on a Windows Server.

The qualitative variables will be described by using usual statistics: population size and percentages (relative to the non-missing data) for each modality. Quantitative variables will be described with the number of observed data, mean, standard deviation (SD), median, and ranges. Two-sided 95% confidence intervals will be presented for relevant variables.

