5.4 SUBGROUPS

Age stratified randomly selected subgroup

In the current dataset, there are 1,823 patients in the bazedoxifene group and 82,041 patients in the bisphosphonate group. This means that there is more than 40 times the number of subjects in the bisphosphonate group compared to the number of subjects in the bazedoxifene group. To limit the number of patients in the bisphosphonate group, an age stratified random subgroup will be selected. Based on the sample size and relative risk estimates provided in the final study protocol (study protocol section 7.1, Sample size calculation), the 1,823 bazedoxifene subjects will be adequately matched by a ratio of 1:6 bisphosphonate subjects. Therefore $1,823 \times 6 = 10,938$ bisphosphonate treated subjects are needed to be randomly selected from the total of 82,041 bisphosphonate treated subjects.

Selection scheme: The age of subjects in the study will be categorized into 4 groups (45-49, 50-59, 60-69, and ≥ 70). In the bisphosphonate group, the percentage of subjects in each of these age groups is 1.4%, 13.7%, 28.7%, and 56.2% respectively. To maintain the same proportion of subjects in each age group for the bisphosphonate subgroup, there will be $1.4\% \times 10,938 = 153$ bisphosphonate treated subjects randomly selected from the 45-49 age group; $13.7\% \times 10,938 = 1,499$ subjects randomly selected from the 50-59 age group; $28.7\% \times 10,938 = 3,139$ subjects randomly selected from the 60-69 age group; $56.2\% \times 10,938 = 6,147$ subjects randomly selected from ≥ 70 age group.

Incident cases of study endpoints

Women with a history of study end points recorded prior to the index prescription will not be included in the analysis for that specific outcome, but will be analyzed separately as subgroups for each study end point. The analyses of the primary and secondary endpoints will be performed using these incident cases of study endpoints subgroups.

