8.1.4 TIME TO EVENT ANALYSIS

A time to event analysis to compare the risk between treatment cohorts, i.e., the BZA, raloxifene and bisphosphonate treated groups, will be conducted for the primary end point (VTE) and other secondary endpoints if sufficient data are available,

[figure not shown]
The time to an event will be calculated as the time from index prescription date to the incidence date of primary end points. If a patient does not have a primary end point, the treatment duration will be based upon the index prescription date to the last visit or end of follow-up period, whichever comes first.

In order to ensure the exact duration from the start of treatment to the incidence of primary endpoints, a subgroup of newly prescribed patients who were diagnosed with osteoporosis during the enrolment period will be used first.

In the very unlikely event that the number of bisphosphonate or raloxifene patients are less than the number of BZA patients, the analysis will be extended to include bisphosphonate and raloxifene patients whose treatment began prior to the enrolment period. Considering the fact that bisphosphonates and raloxifene were launched before BZA (See the figure below), some patients could have already gotten treatment of bisphosphonates and raloxifene prior to the enrolment period (i.e., before BZA was launched). For such patients the start date will be the first date of treatment for bisphosphonates or raloxifene, available within the database.

Figure 1. Calculation of duration (from start date to the incidence of primary endpoint) for the treatment cohorts

The time to event analysis model will also be used to test for differences in time to event while adjusting for covariates of interest.

This model will take into account the duration to the incidence of the endpoint and control for imbalances in outcome risk factors, as determined based on the baseline descriptive analysis.

The following factors possibly related to the incidence of the primary end point will be considered.

- Treatment group (BZA, raloxifene, and bisphosphonate)
- Age
- BMI
- Reported history of smoking (If the reported frequency of smoking status is low this will be excluded)
- Reported Medical History of Diabetes, Hypertension, Malignancies
- Time since diagnosis of osteoporosis
- Previous treatment for osteoporosis (before index date) or Number of different treatments for osteoporosis in the entire patient history available
- History of DVT or PE

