- Previous history of major lower extremity (hip, knee) arthroplasty, arthroscopic surgery (information on arthroscopic surgery not available in Italian database)
- General surgery, major orthopedic surgery (<1month prior to incidence of VTE)
- (Information on general surgery not available in Italian database)
- Multiple trauma (<1month prior to incidence of VTE)
- Hip, pelvis, or leg fracture (<1month prior to incidence of VTE)
- Stroke (<1month prior to incidence of VTE)
- Acute spinal cord injury (paralysis) (<1month prior to incidence of VTE)
- Hormone replacement therapy (limited information available in both databases)

A Cox model will be used in order to take into account the time varying component. The time from the beginning of the treatment (one among three types, BZA, raloxifene, and bisphosphonate) to the occurrence of primary end point is fitted in this model. The Proportional Hazards (PH) assumption will be tested for each covariable. If the PH assumption does not hold for some covariates, the use of time-varying HR for those covariates will be explored. If a categorical variable with more than 2 levels does not satisfy this PH assumption, collapsing some categories will be attempted to satisfy the PH assumption. Correlations between variables will also be evaluated in order to find independent factors and a final model that is clinically relevant.

First, the univariate analysis will be carried out on each covariable in order to determine the explanatory variables to be included in the final multivariate model. All significant variables with a p -value ≤ 0.20 in the univariate model will be taken into account in the multivariate Cox model.

If > 80% of the important risk factors for VTE listed above does not satisfy the PH assumption, a logistic regression analysis would be performed instead of Cox model to otherwise determine if the covariable is related to the incidence primary endpoint (VTE). The dependent variable would be the incidence of the primary end point during the follow-up period categorized as a binary variable. The 2 indicators of treatment group (BZA vs. bisphosphonates, raloxifene, will be forced in the multivariate model (Cox model or logistic model) to analyze incidence in each class of treatment, adjusted on

significant factors. Hazard ratios (HR) (odds ratios (OR) in case of logistic regression) with 95% Confidence intervals (CIs) and p-values will be presented.

[figure not shown]
Patients Switching Medications

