8.2.4 TIME TO EVENT ANALYSIS

Time to event analysis will be conducted as a secondary analysis and the following factors possibly related to incidence of end points will be considered at the date of Incidence or the last visit before incidence: age, BMI, smoking (depending on availability of data), history of diabetes, history of hypertension, history of malignancies, history of VTE, and some other co-morbidities. Univariate Cox models (if applicable, depending on the PH assumptions for each factor, otherwise logistic regression model) will be performed for each factor and then, the analysis will be complemented by a multivariate Cox model (if applicable, depending on the PH assumptions for each factor) or a logistic regression. Hazard ratios (HR) or odds-ratios with 95% CI and p-values will be presented for significant factors at the 0.05 level.

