8.2.5 SUMMARY OF STATISTICAL ANALYSIS

Analyses for Primary Objective and Secondary Objective 1

Comparator: BZA vs. bisphosphonate (primary objective), BZA vs. raloxifene (secondary objective 1).

Study endpoint: VTE.

Populations: a. Full BZA full raloxifene, random age stratified bisphosphonate subgroup
b. Incident user subgroup.

Statistical Method:

- i. Incidence rate, cumulative method (*Total new cases during follow-up period / Total persons at risk during follow-up period*) with stratification by risks of interest e.g. Age, BMI.
- ii. Univariate and multivariate incidence rate by incidence density (*Total new cases during follow up period / Total person years during follow-up period*)*1000) method using Cox regression model and a Likelihood Ratio Test for testing Hazard Ratio (HR) =1 (ratio of hazard in BZA population vs. bisphosphonate/raloxifene population) with covariates associated with VTE outcome and exposure (Drug groups).

Sensitivity analyses:

- i. Repeat analysis will be conducted that compares using a 30-day and a 90-day definition of recent exposure with using the 60-day definition.
- ii. Missing Data: First, the analyses will be repeated utilizing a complete dataset in which cases with missing values of main study covariates of BMI, smoking status and alcohol status have been deleted. Second, multiple imputation for the missing values of BMI, smoking status, alcohol status will be used in the second set of analyses.

Multiple imputation procedure:

- 1) Estimate distribution of BMI, smoking status and alcohol status according to patients whose data are available.
- 2) For the patients who had missing values those variables draw values of the variables from the distribution from 1).
- 3) With the imputed dataset (including none-missing data), estimate HR as described.
- 4) Repeat 2)-3) for m times, and record HR of each time.
- 5) Calculate mean of m estimates of HR.
- 6) Adjust variance of HR with the following formula, and use the variance to calculate confidence interval.

$$V = \left(1 + \frac{1}{M}\right) V_B + V_W.$$

V_B is the between imputation variance, and V_W is within imputation variance.

Analyses for Secondary Objective 2 and Secondary Objective 3

Comparator: BZA vs. bisphosphonate (secondary objective 2), BZA vs. raloxifene (secondary objective 3).

Study endpoint: Secondary endpoints.

Population: a. Full BZA, full raloxifene, random age stratified bisphosphonate subgroup.
b. Incident user subgroup

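### The pooled bazedoxifene comparisons are open to confounding by country: bazedoxifene users are about 98% Spanish, yet the SAP names no country stratum or covariate and draws bisphosphonate comparators by age alone

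*SAP*

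**What the plan says.** SAP 8.1 plans a report in three parts: "one part for Italy, one part for Spain, and the final part with pooled data of both countries". For the third part, "Pooling of data for the combined results of Italy and Spain will be done at the patient level". The same section requires confounding in the pooled data to be handled by the method used within each country, and describes accrual with the words "Given the very low enrolment from Italy (approximately 40 patients, vs. approximately 1700 from Spain".

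SAP 5.4 gives 1,823 bazedoxifene and 82,041 bisphosphonate patients and cuts the latter to 10,938: "To limit the number of patients in the bisphosphonate group, an age stratified random subgroup will be selected". The only strata are four age bands, filled in the bisphosphonate cohort's own age proportions.

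The covariates are described in three places, none of which names country:
- SAP 8.1.4 introduces its list with "The following factors possibly related to the incidence of the primary end point will be considered".
- SAP 8.2.4 gives a shorter list ending "history of malignancies, history of VTE, and some other co-morbidities".
- SAP 8.2.5 asks for Cox models "with covariates associated with VTE outcome and exposure (Drug groups".

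Covariate capture also differs by country. SAP 8.1.4 notes "Information on general surgery not available in Italian database" and says the same of arthroscopic surgery. SAP 8.2.1 treats any listed condition that is not found as absent.

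**The concern.** Country is almost a proxy for bazedoxifene. If the comparators have a different country mix, anything that differs between the two databases becomes attached to the treatment contrast in the pooled part. That includes true VTE incidence, how hospital-diagnosed VTE reaches the GP record, the coding system (ICD-9 in Italy, ICPC in Spain) and length of follow-up.

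The exposure is not limited to the Cox model. SAP 8.1.2 makes cumulative incidence the primary calculation. That is a simple ratio of cases to persons, with stratification by risk factors such as age or BMI, so differences in follow-up enter it directly and a Cox covariate cannot repair it.

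A method that works within one country has no country term, because country is constant there. Carried over unchanged to pooled data, it leaves the country difference unadjusted. The surgery covariates make this worse: if unavailable procedures are coded absent for Italian women, those covariates are misclassified by country.

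Finally, the SAP does not say which of the three parts governs. If the Spain-only and pooled results disagree, the reader has no rule for choosing between them.

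**Working it through.** **1. The plan's own sample.** 1,823 × 6 = 10,938. Applying 1.4%, 13.7%, 28.7% and 56.2% gives 153, 1,499, 3,139 and 6,147. These match SAP 5.4.

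**2. Country mix of bazedoxifene users.** 1,700 / (1,700 + 40) = 97.7% Spanish, so the Italian share is b = 40/1,740 = 2.3%. The counts sum to 1,740, which is 83 short of 1,823. If all 83 were Italian, b = 123/1,823 = 6.7%.

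**3. Could the bisphosphonate cohort have the same mix?** It would need 82,041 × 0.977 = 80,155 Spanish women. The Spanish panel sees 320,000 patients a year, of both sexes and all ages (SAP 2.1, panel table). 80,155 / 320,000 = 25%, which is implausible. The Italian panel sees 800,000. The actual split is not given, so I take Italian comparator shares s of 30%, 50% and 800/1,120 = 71.4% (the panel mix).

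**4. Crude pooled ratio when the true ratio is 1.** With x the Italy:Spain ratio of recorded VTE rates (assumed), the ratio is [(1 − b) + b·x] / [(1 − s) + s·x]. At b = 2.3%:

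| s | x = 0.5 | x = 0.8 | x = 1 | x = 1.25 | x = 2 |
|---|---|---|---|---|---|
| 30% | 1.16 | 1.06 | 1.00 | 0.94 | 0.79 |
| 50% | 1.32 | 1.11 | 1.00 | 0.89 | 0.68 |
| 71.4% | 1.54 | 1.16 | 1.00 | 0.85 | 0.60 |

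At b = 6.7% and s = 71.4%, the extremes are 1.50 and 0.62. If s = b, the ratio is 1.00 for any x.

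**5. What the age-only draw leaves for Spain.** In expectation it keeps the cohort's country mix, so Spanish comparators number 10,938 × (1 − s). Precision uses SE(log IRR) = √(1/E₁ + 1/E₂) with Wald 95% limits, 1.74 VTEs per 1,000 person-years and a true IRR of 2. Five years with 15% annual loss gives (1 − 0.85⁵)/(−ln 0.85) = 3.42 person-years per woman.

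| Comparison | Ratio | SE | 95% CI at IRR 2 |
|---|---|---|---|
| Unstratified, 1,740 vs 10,938 | 1:6.3 | 0.252 | 1.22–3.28 |
| Spain, 1,700 vs 3,125 (s = 71.4%) | 1:1.8 | 0.321 | 1.07–3.75 |
| Spain, 1,700 vs 5,469 (s = 50%) | 1:3.2 | 0.283 | 1.15–3.48 |
| Spain, 1,700 vs 7,657 (s = 30%) | 1:4.5 | 0.267 | 1.19–3.38 |
| Spain, 1,700 vs 10,200 (1:6 within Spain) | 1:6 | 0.257 | 1.21–3.31 |

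This follow-up figure gives 1.22–3.28 for Protocol Table 3's 1,750:10,500 row, where the table prints 1.3–3.1. About 4.35 person-years per woman fits that table better. With it, the Spain-only intervals are 1.14–3.50 (3,125 comparators), 1.22–3.27 (5,469) and 1.28–3.13 (10,200). Ratios of SEs do not depend on this choice.

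**6. Cost in precision at IRR 2.** 0.321/0.252 = 1.27 with the age-only draw at panel mix, and 0.257/0.252 = 1.02 with a 1:6 draw within Spain. At IRR 1 the first figure is 0.390/0.334 = 1.17.

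**7. Are there enough Spanish women?** 1,700 × 6 = 10,200 are needed. They exist unless more than 1 − 10,200/82,041 = 87.6% of the cohort is Italian.

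**8. Italy alone.** 40 × 3.42 × 0.00174 = 0.24 expected VTEs among bazedoxifene users at IRR 1.

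**The case against.** The strongest reply is that the design already contains the answer. Protocol 7.2 and SAP 8.1 both require a separate Spain analysis, which holds nearly all bazedoxifene users and is free of this bias. That stands, and it confines the problem to the pooled part. It does not settle the matter, because the SAP neither makes the Spain-only result the lead nor protects its comparator ratio.

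SAP 8.1 also promises a confounding assessment for the pooled data, SAP 8.1.4 promises control of baseline imbalances, and the criterion in SAP 8.2.5 could admit country. These make the gap an under-specification rather than a decision to ignore confounding. But no text names country, and the instruction to use the same method in single-country and pooled data points the other way.

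Code harmonisation, reporting of unmapped codes and expert review of identified cases reduce coding differences. They cannot recover unrecorded events or remove real differences in rates.

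Four technical points are fair:
- The age-only draw does not create the imbalance; it carries the existing one forward and can thin the Spanish comparator.
- The ratios in the table are crude, and covariate adjustment may absorb part of a real country difference.
- The widest range combines an Italian share taken from all GP consulters with a twofold rate difference. Rate ratios of 0.8 to 1.25 give 1.16 to 0.85 at the same share.
- Both country counts are approximate, so the shortfall of 83 is a point to reconcile, not evidence of an error.

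**Conclusion.** The concern holds. Followed as written, the plan leaves the pooled rate ratios, cumulative-incidence comparison and hazard ratios open to between-country confounding. Confidence is high about the omission and the imbalance among bazedoxifene users. It is low about the size of the bias, because the documents give neither the comparators' country split nor VTE rates by country. Under the assumptions shown, a true ratio of 1 could appear as anything from 1.54 to 0.60, and there is no bias if either the rates or the mixes are equal. The protocol's planning ratios are 1, 1.5 and 2, so the upper end would pass for a real signal and the lower end could hide one. The Spain-only part is a real but unprotected safeguard. This should be fixed, but it does not invalidate the study.

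**What to change.** - Stratify every pooled Cox model by country, and use country-stratified rate and risk ratios (for example Mantel-Haenszel). Given a common ratio in both countries, this removes the between-country component. The raloxifene cohort is used in full, so the stratum is its only protection.
- Draw bisphosphonate women within country and age band at 1:6 to that country's bazedoxifene count: about 10,200 Spanish and 240 Italian women.
- Tabulate all three cohorts by country.
- Use the general and arthroscopic surgery covariates only in Spain.
- Name the Spain-only result as the key reading, reported beside the country-stratified pooled result. The two will be close, since both rest almost wholly on Spanish data.
- Reconcile 1,740 with 1,823 and update the draw accordingly.

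The cost is SAP wording, a stratum statement in the models and a new comparator draw. At IRR 2 the standard error rises by about 2% with the 1:6 draw within Spain. Stratifying without redrawing would raise it by about 27% if comparators follow the panel mix (about 17% at IRR 1).

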8.1.1 PATIENT CHARACTERISTICS

The following characteristics will be reported for all treatment cohorts at baseline.

- Demographic Characteristics: Age, BMI, Smoking

Age (years) at index date will be calculated as Age = year (index date)-year (birth).

Four age groups are defined (in years): 45-49, 50-59, 60-69 and 70 and over.

BMI (Body Mass Index) will be calculated for each patient as the weight in kg divided by square of height in meters. BMI will be calculated using the following formulas:

$$BMI (kg/m^2) = Weight (kg) / (Height (m))^2$$

Or

$$BMI (kg/m^2) = 10000 \times Weight (kg) / (Height (cm))^2$$

- BMI will be categorized into four groups as follows:
- Underweight: BMI <18.5 kg/m²
 - Normal range: 18.5 ≤ BMI <25 kg/m²
 - Overweight: 25 ≤ BMI <30 kg/m²
 - Obese : BMI ≥30 kg/m²
- Smoking will be defined as three categories; Current Smokers, Former Smokers and Never Smokers. A 'Current Smoker' will be defined as a patient who is currently smoking at the index prescription date, a 'Former Smoker' as a patient that has a past history of smoking but has stopped prior to the index prescription date. A 'Never Smoker' will be defined as a patient that has no history of smoking (The reported frequency of smoking may be very low because smoking status is under recorded in Italian and Spain databases)
 - Alcohol use. Alcohol use will be defined as three categories; Current Drinkers, Former Drinkers and Never Drinkers. A 'Current Drinker' will be defined as a patient who is currently drinking alcohol as at the index prescription date, a 'Former Smoker' as a patient that has a past history of drinking alcohol but has stopped drinking prior to the index prescription date. A 'Never Drinker' will be defined as a patient that has no history of drinking alcohol. (The reported frequency of alcohol use may be very low because alcohol use is under recorded in Italian and Spain databases).
 - Use of relevant concomitant medications, e.g., hormone replacement therapy. (A concomitant medication is any medication used during BZA/bisphosphonate/raloxifene treatment defined as the total treatment duration between the first and the last prescription of BZA/bisphosphonate/raloxifene.)
 - Medical History VTE (Venous Thromboembolic Events), Diabetes, Hypertension, and Malignancies (including Breast, Renal, Thyroid, Ovarian, Gastrointestinal tract, Lung) and aggregate of all malignancies.

Venous Thromboembolic Events (VTE) are defined as deep vein thrombosis, pulmonary embolism, retinal vein thrombosis, and venous sinus thrombosis. This objective is to compare this incidence in real life settings with validated diagnosis codes, ICD9 in Italy and International Classification of Primary Care (ICPC) codes in Spain.

The availability of medical history of all relevant medical diagnosis for patients will be checked in both the Spanish and the Italian database and presented if available. The variables of medical history (diabetes, hypertension, VTE and Malignancies) will be presented in classes (Yes/No) before index date. (All the detailed diagnosis codes of each endpoint have been validated by Pfizer and are available in a separate reference document). For all medical history and smoking status, if the relevant information is not found in the database, it will be assumed to be negative.

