8.1.2 INCIDENCE RATES

Incidence rates will be calculated for all endpoints in all cohort groups; incidence rate ratios and 95% confidence intervals will be calculated as specified previously.

The incidence rate for all end points will be calculated using both the cumulative incidence approach and an incidence density (person-time) approach. The cumulative incidence approach will be used as the primary analysis and it will be calculated as in the following formula:

$$\text{Incidence rate} = (\text{Total new cases during follow-up period} / \text{Total persons at risk during follow-up period})$$

For this study, the numerator will be defined as the total number of patients with a diagnosis of primary end points or secondary end points during follow-up period. The denominator will be the total number of all patients at risk in cohorts groups during follow-up period.

Secondly, an incidence density approach calculates time at risk in person-years, measured from first prescription to the end of the observation period. The incidence rate will be reported as per 1,000 person-years of observation as shown in the following formula:

$$\text{Incidence Rate} = (\text{Total new cases during follow up period} / \text{Total person years during follow-up period}) * 1000$$

The numerator will be defined as the total number patients with end points of interest during follow-up period. The denominator will be defined as the sum of person years of patients during the follow up period. For patients who have incidence of primary or secondary end points, person time will equal the sum of days from their first prescription of treatment (index prescription) until the date of the incident condition (diagnosis of primary or secondary end points). For patients who do not experience an incidence of primary or secondary end points, person time will equal the sum of days from their first prescription of treatment (index prescription) to the last visit date or completion of 5 years follow up at which all patients will be censored, whichever occurs first.

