In the determination of person years, the date of first prescription of treatment will be used as a surrogate for time of first exposure to treatment, since the date when the patient had their first treatment for osteoporosis may not be consistently ascertainable. The same definition of person-time ('ever' exposed approach accounting for all person-times of exposure) will be used for all the study endpoints given that they are all chronic diseases or malignancies with potentially long latency periods. If no primary end point occurs during the follow-up period, the duration will be calculated from the start of treatment date to the last patient visit or the end of study period, whichever comes first.

Both methods of calculating incidence rates will be used and the number of patients for whom the date of first treatment for osteoporosis could not be ascertained will be provided as part of the sensitivity analysis of the incidence density approach.

Stratifications by risks of interest (e.g. age, BMI, or selected medical history) will be performed for each outcome and descriptive summaries will be reported. For example, VTE incidence will be stratified according to age as well as by BMI. Other stratifications by medical co-morbidities and other variables of interest will also be performed as appropriate.

Given the rarity of certain malignancies in this population, the incidence rates observed in this study may be small and imprecise. To better characterize the rates obtained in this study, an additional analysis using external reference data for the malignancies will be conducted, i.e. a standardized incidence ratio (SIR). The observed frequency of malignancies in all three treatment groups will be compared with the expected frequency calculated from an age and gender matched population-based reference group (e.g., GloboCan). This SIR of observed versus expected events and 95% confidence interval, will be reported.

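### The SAP's only age categories end in one open band of 70 and over, holding 56.2% of bisphosphonate women, and no planned step guarantees finer control for age in the VTE comparison

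*SAP*

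**What the plan says.** SAP 8.1.1 sets the age categories: "Four age groups are defined (in years): 45-49, 50-59, 60-69 and 70 and over". SAP 5.4 uses the same four bands to draw the bisphosphonate subgroup and reports that in the bisphosphonate cohort "the percentage of subjects in each of these age groups is 1.4%, 13.7%, 28.7%, and 56.2% respectively". The draw is proportional to that cohort's own age mix ("To maintain the same proportion of subjects in each age group for the bisphosphonate subgroup").

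On the analysis, SAP 8.1.2 says "The cumulative incidence approach will be used as the primary analysis". Age enters that method only by stratification: "Stratifications by risks of interest (e.g. age, BMI, or selected medical history) will be performed for each outcome and descriptive summaries will be reported", with the example that "VTE incidence will be stratified according to age as well as by BMI". SAP 8.2.5 repeats the pairing of the cumulative method with stratification by age and BMI. No cut-points are given in either place, so the 8.1.1 bands are the only ones available.

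The Cox hazard ratio is named as the comparison tool in SAP 4.2 and 8.2.2, while SAP 8.2.4 calls the time-to-event analysis secondary. SAP 8.1.4 and 8.2.4 list age among the factors to be considered but do not say whether it is continuous or banded. Under 8.1.4, covariates reach the multivariable model by a univariate p-value of 0.20 or less, and only the treatment indicators are forced in. Age itself is derived in whole years (SAP 8.1.1 and 8.2.1) and is known for every woman (SAP 7).

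**The concern.** A stratified comparison removes confounding between strata, not within them. Here more than half of the comparator cohort sits in one stratum with no upper limit, so women of 71 and 91 count as the same age in any table built on these bands. The SAP itself treats age as a factor possibly related to VTE. If bazedoxifene and bisphosphonate women differ in age within the top band, the ratio of their rates there mixes drug and age. In a post-authorisation safety study, the costly case is younger bazedoxifene women, because that would pull the ratio down and could mask a VTE excess. Older bazedoxifene women would create an apparent excess.

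**Working it through.** **1. The plan's own figures reproduce.** By SAP 5.4, 1,823 × 6 = 10,938. Applying the shares:

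| Band | Share | Share × 10,938 | SAP |
|---|---|---|---|
| 45-49 | 1.4% | 153.1 | 153 |
| 50-59 | 13.7% | 1,498.5 | 1,499 |
| 60-69 | 28.7% | 3,139.2 | 3,139 |
| 70 and over | 56.2% | 6,147.2 | 6,147 |

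**2. Events in the top band.** Inputs are the comparator rate of 1.74 per 1000 patient-years (protocol 7.1) and an assumed 4.25 patient-years per woman. The latter is 5 × 0.85, from the 5-year follow-up and 15% loss; it is not stated, but it reproduces 22 of the 24 limits in protocol Table 3.

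- All sampled bisphosphonate women: 10,938 × 4.25 × 0.00174 = 80.9.
- Aged 70 and over: 6,147 × 4.25 × 0.00174 = 45.5, which is 56.2% by construction because the rate is flat.

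If the rate multiplies by r per decade, the band's share of events is its weight divided by the sum of weights, where weight = share × r^((mid-age − 65)/10). With assumed mid-ages of 47.5, 55, 65 and 78, the share is 65% for r = 1.25, 71% for r = 1.5 and 79% for r = 2.

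**3. Possible bias inside the band.** With a true ratio of 1 and bazedoxifene women g years older than bisphosphonate women within the band (g negative if younger), the apparent ratio is approximately r^(g/10). Both r and g are assumptions.

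| g (years) | r = 1.5 | r = 2 |
|---|---|---|
| −5 | 0.82 | 0.71 |
| −2 | 0.92 | 0.87 |
| 0 | 1.00 | 1.00 |
| +2 | 1.08 | 1.15 |
| +5 | 1.22 | 1.41 |

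**4. What a split recovers.** Take ages 70 to 95 with frequencies proportional to exp(−k(age − 70)). Use k = 0.10, 0.15 and 0.20 for bazedoxifene against 0.06, 0.06 and 0.05 for bisphosphonate, which makes the bazedoxifene women younger by 1.8, 3.6 and 5.4 years on average. The true ratio is 1. The table shows observed over expected bazedoxifene events, where expected applies the bisphosphonate rate in each band to the bazedoxifene women in that band. Ranges run over r = 1.5 to 2.

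| Bands | Gap 1.8 y | Gap 3.6 y | Gap 5.4 y |
|---|---|---|---|
| 70 and over | 0.92 to 0.87 | 0.85 to 0.75 | 0.78 to 0.64 |
| 70-79, 80 and over | 0.98 to 0.96 | 0.96 to 0.93 | 0.94 to 0.90 |
| 70-74, 75-79, 80-84, 85 and over | 0.99 to 0.99 | 0.99 to 0.98 | 0.99 to 0.97 |

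A single-year age term of the right shape gives 1.00.

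**5. Does any planned step guarantee finer control?**

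- *Stratified rates:* the only bands defined end at 70 and over.
- *Cox model:* age may enter in single years, may enter as the four bands, or may fail the 0.20 screen. If a banded term fails proportional hazards, SAP 8.1.4 would first try collapsing categories, which makes it coarser.
- *Sampling:* it reproduces the bisphosphonate age mix and does not target the bazedoxifene one.

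So none does.

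**The case against.** The strongest reply is that the bands are not the plan's confounder control. Age is a candidate Cox covariate, it is derived in whole years, the Cox hazard ratio is the stated tool for comparing rates, and SAP 8.1.2 describes the stratified results as descriptive. A reader might infer from the four bands that all age control runs through them. The documents do not support that, since the Cox age term could well be continuous. What remains is that its form is unstated, its inclusion is not assured, and the method called primary has nothing else for age.

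A reader might also infer that the comparison is in fact confounded, or that a VTE excess will be hidden. That is not supported either. It needs an age gap within the band, and the documents give no bazedoxifene age distribution. Protocol section 10 raises the possibility of a younger cohort only for raloxifene. The bias could run either way or be nil. That most events fall at 70 and over is a fair inference for the bisphosphonate arm if VTE risk does not fall with age, but it is not stated.

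Finer bands also cost precision. At a ratio of 1 the 1,823 bazedoxifene women expect 1,823 × 4.25 × 0.00174 = 13.5 events, or 10.9 at 3.42 patient-years (continuous loss at 15% a year). If 56.2% of them were 70 or over (an assumption), that is 6 to 8 events in the band, and about 2 in each of four sub-bands on average. This stands, and it argues for a modest split.

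**Conclusion.** The point holds as a gap in specification. The documents establish that the top band is open, that it contains 56.2% of bisphosphonate women, that the primary cumulative-incidence method has no other age handling, and that the Cox age term has neither a stated form nor a guaranteed place. They do not establish that bias exists, or its direction. The ratios of 0.92 to 0.71 (younger bazedoxifene women) and 1.08 to 1.41 (older) are illustrations that rest on an assumed 1.5 to 2 fold rise in risk per decade and an assumed 2 to 5 year gap within the band; with no gap the ratio is 1.00. The change is still worth making, because age is available for every woman and the remedy is cheap.

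**What to change.** 1. In SAP 8.1.1 and 8.1.2, split the top band for the stratified rates into at least 70-79 and 80 and over, and finer where event counts allow.
2. In SAP 8.1.4 and 8.2.4, state that age enters the Cox model as a continuous term, for example a spline on age in years, and is always included whatever the univariate screen shows.

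The cost is SAP wording and a few more table rows, some with very few bazedoxifene events, particularly in the country-specific tables.

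Two neighbouring changes are not needed for this purpose. Splitting the sampling bands would leave the balance between bazedoxifene and bisphosphonate unchanged, because the draw follows the bisphosphonate cohort's own age mix. Merging 45-49 with 50-59 would not reduce confounding.
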